2.1.4.2 Adverse events variables

Adverse event observation period

- Pretreatment adverse events are adverse events that developed or worsened or became serious from the signed informed consent date up to first administration of double-blind IMP.
- Treatment-emergent adverse events are adverse events that developed or worsened or became serious during the TEAE period.
- Posttreatment adverse events are adverse events that developed or worsened or became serious during the posttreatment period.

All adverse events (including SAE, AESI and EOSI) will be coded to a lower-level term (LLT), preferred term (PT), high-level term (HLT), high-level group term (HLGT), and associated primary system organ class (SOC) using the version of Medical Dictionary for Regulatory Activities (MedDRA) currently in effect at Covance at the time of database lock.

The occurrence of adverse events (including SAE, AESI and EOSI) will be recorded from the time of signed informed consent until the end of the study (see [Section 2.1.4](#)) or the resolution/stabilization of all SAE, AESI and EOSI.

AESI include:

- Pregnancy.
- Symptomatic overdose with IMP/NIMP.
- Alanine aminotransferase (ALT) increase >3 times upper limit of normal (ULN).

EOSI include:

- Major adverse cardiovascular events (MACE [cardiovascular death, myocardial infarction, or stroke]) and other specific cardiovascular (CV) events (eg, heart failure requiring hospitalization).
- Severe hypoglycemia.
- Genital mycotic infections (to include vulvovaginal candidiasis in females and candida balanitis in males).
- Urinary tract infection.
- Clinically relevant volume depletion and events related/possibly related to volume depletion.
- Diarrhea.
- Pancreatitis.
- Bone fractures.

- Venous thrombotic events, to include deep venous thrombosis and thromboembolism (to include pulmonary embolism).
- Diabetic ketoacidosis (DKA).
- Renal events, to include 50% decline in eGFR, end stage kidney disease, renal death.
- Malignancies of special interest (breast, bladder, renal cell, Leydig cell, pancreatic, prostate, and thyroid cancer).
- Adverse event leading to an amputation.

A Clinical Endpoint Committee(s) (CEC) will, in a blinded manner, review and adjudicate all deaths, myocardial infarction, stroke, unstable angina requiring hospitalization, and heart failure requiring hospitalization, selected renal events, bone fracture, and DKA.

Two independent committees will review safety events that require ongoing monitoring in a blinded manner. These events are: 1) potential cases of drug-induced liver injury (DILI), and 2) cases of amputations. The two committees will review the cases in a treatment-blinded manner and will present their assessment to the DMC.

AESI and EOSI will be identified based on criteria in [Table 2](#).

Table 2 – Criteria for AESI and EOSI

AE Grouping	Criteria
AESI	
Pregnancy	eCRF "Pregnancy"
Symptomatic overdose with IMP/NIMP	"Overdose of IMP" or "Overdose of NIMP" checked and "Symptomatic overdose" checked in eCRF "Overdose"
ALT increase > 3X ULN	eCRF "ALT increase"
EOSI adjudicated	
Cardiovascular death	Positively adjudicated by CEC: "Cardiovascular" or "Undetermined" as the primary cause of death
Myocardial infarction, Unstable Angina requiring hospitalization	Positively adjudicated by CEC: Yes to the question "Does the event meet the definition of an MI for this study?", or Yes to the question "If event is not an MI, does the event meet the definition of an UA Requiring admission to hospital or emergency room, for this study?"
Stroke	Positively adjudicated by CEC: Yes to the question "Does the event meet the definition of a Stroke for this study?"
Heart failure requiring hospitalization	Positively adjudicated by CEC: Yes to the question "Does the event meet the definition of a Heart Failure Event for this study?"
Bone fractures	Positively adjudicated by CEC: Yes to the question "Did the Fracture occur?"
Diabetic ketoacidosis	Positively adjudicated by CEC: Yes to the question "Does this event meet the criteria to be a DKA event?"

AE Grouping	Criteria
EOSI Renal events where select events adjudicated	
Sustained $\geq 50\%$ decrease in eGFR	(1) For $\geq 50\%$ decrease in eGFR from Baseline, (1a) confirmed $\geq 50\%$ decrease in GFR for ≥ 30 days with no reversible cause as recorded in eCRF "eGFR decrease", OR (1b) positively adjudicated by CEC: Yes to the question "Does the subject meet the criteria of CKD progression" for $\geq 50\%$ decrease in eGFR.
Sustained eGFR < 15 mL/min/1.73 m ²	(2) For eGFR < 15 mL/min/1.73 m ² , (2a) confirmed eGFR < 15 mL/min/1.73 m ² for ≥ 30 days with no reversible cause as recorded in eCRF "eGFR decrease", OR (2b) positively adjudicated by CEC: Yes to the question "Does the subject meet the criteria of CKD progression".
Chronic dialysis	(3) For dialysis, (3a) dialysis lasted for ≥ 90 days (eg, end date – start date+ 1 ≥ 90) as recorded in eCRF "Renal Event – Dialysis", OR (3b) positively adjudicated by CEC: Yes to the question ". Does the subject meet the criteria for ESRD".
Renal transplant *	(4) "Renal transplant" captured in eCRF "Other procedure form", where adjudication is not required. PTs of Renal transplant (10038533), Renal and pancreas transplant (10052278), Renal and liver transplant (10052279) based on MedDRA v22.0.
Renal death	(5) Renal death as positively adjudicated by CEC: "Death - Non-Cardiovascular (Renal)" as the primary cause of death
EOSI not adjudicated*	
Severe hypoglycemia	algorithm specified in Section 2.1.4.1 based on eCRF "Hypoglycemic Events"
Genital mycotic infections	PTs in Appendix B
Urinary tract infections	PTs in Appendix B
Clinically relevant volume depletion and events related/possibly related to volume depletion	PTs in Appendix B
Diarrhea	Narrow search on "Noninfectious diarrhoea (SMQ)" [20000218] plus the following PTs (MedDRA v22.0): Gastroenteritis (10017888), Antidiarrhoeal supportive care (10055660), Enteritis (10014866), Enteritis leukopenic (10014877), Enterocolitis (10014893), Enterocolitis haemorrhagic (10014896)
Pancreatitis	PTs in Appendix B
Venous thrombotic events	PTs in Appendix B

AE Grouping	Criteria
Malignancies of special interest	Breast cancer: Narrow search on “Breast neoplasms, malignant and unspecified (SMQ)” [20000149] Prostate cancer: Narrow search on “Prostate neoplasms, malignant and unspecified (SMQ)” [20000152] Leydig-cell cancer: PTs of Leydig cell tumour of the testis (10024407) and Ovarian Sertoli-Leydig cell tumour (10073270) based on MedDRA v22.0 Thyroid cancer: PTs in Appendix B Renal cell cancer: PTs in Appendix B Pancreatic cancer: PTs in Appendix B Bladder cancer: PTs in Appendix B

EOSI AE leading to an amputation

AE leading to an amputation	“AE Correction” as the reason for amputation in eCRF “Other Procedures related to Amputation”
AE potentially leading to an amputation *	PTs in Appendix B

* Search terms will be updated using the MedDRA version currently in effect at Covance at the time of database lock for EOSI identified by them.

* AE potentially leading to amputation: not one of EOSI defined in protocol, included and analyzed due to their relevance in regards to lower limb complications and amputations as an requirement from health authorities.

2.1.4.3 Deaths

The death observation periods are per the observation periods defined below.

- Death on-study: deaths occurring during the on-study observation period.
- Death on TEAE period: deaths occurring during the TEAE period.
- Death post-treatment: deaths occurring after the treatment-emergent adverse event period until the end of the on-study period.

2.1.4.4 Laboratory safety variables

Clinical laboratory data consists of blood analysis, including hematology, clinical chemistry, amylase, lipase, lipide profile and urinalysis. Clinical laboratory values after conversion will be analyzed into standard international units and conventional units when applicable.

Blood samples for clinical laboratories will be collected at designated visits (see study flowchart in Appendix D). The following laboratory data will be measured at a central laboratory:

- Hematology:
 - **Red blood cells and platelets:** hemoglobin, hematocrit, red blood cell, platelets count,
 - **White blood cells:** white blood cell, neutrophils, lymphocytes, monocytes, basophils, eosinophils.
- Clinical chemistry:
 - **Metabolism:** glucose (serum), creatine phosphokinase (CK),
 - **Electrolytes and minerals:** sodium, potassium, chloride, bicarbonate (ie, carbon dioxide), calcium, phosphorus, magnesium,
 - **Renal function:** blood urea nitrogen (BUN), creatinine, uric acid,
 - **Liver function:** total protein, albumin, alanine aminotransferase (ALT), aspartate aminotransferase (AST), alkaline phosphatase (ALP), total bilirubin (TB), Lactic acid dehydrogenase (LDH).
- Lipid parameters (fasting): total cholesterol (TC), high density lipoprotein cholesterol (HDL-C), low density lipoprotein cholesterol (LDL-C) (calculated by Friedwald equation, See [Section 2.5.1](#)), Non-HDL-C (calculated as the difference between TC and HDL-C), triglycerides (TG).
- Pancreatic enzymes: lipase, amylase.
- Markers of bone and calcium metabolism:
 - Calcium,
 - Phosphorus,
 - Magnesium
 - 25-hydroxyvitamin D,
 - 1,25-dihydroxyvitamin D,
 - Parathyroid hormone (PTH),
 - Markers of bone resorption: N-terminal telopeptide (NTX), beta-C-terminal telopeptide (β -CTX-1),
 - Marker of bone formation: Type 1 procollagen N-terminal (P1NP), osteocalcin.

Urine samples will be collected at designated visits (see study flowchart in Appendix D). The following laboratory data will be measured at a central laboratory:

- Urine dipstick includes: specific gravity, pH, protein, blood, ketones, bilirubin, urobilinogen, nitrite, and leukocyte esterase.
- Urine microscopy includes, but is not limited to: detection of formed cellular elements, casts, bacteria, yeast, parasites, and crystals in centrifuged urine sediment.
- Urine albumin, calcium, phosphorus, magnesium and creatinine (24-hour urine collection).

Serum glucose, calculated UACR and serum estradiol (for women) will be presented as efficacy parameters in [Section 2.4.4](#). For creatinine and calculated eGFR, Potentially Clinically Significant Abnormality (PCSA) summaries will be presented in the safety section while descriptive summaries in the efficacy section.

Technical formulas are described in [Section 2.5.1](#).

2.1.4.5 Vital signs variables

Vital signs include: heart rate (HR), systolic and diastolic blood pressure, temperature, and respiratory rate (see study flowchart in Appendix D for designated visits). They will be performed after the patient has been seated for at least 5 minutes. Blood pressure and HR will be assessed 3 times with at least 1 minute between each measurement following the 5-minute rest period. The mean of the 3 measurements will be analyzed for each vital sign variable (HR, SBP, and DBP).

2.1.4.6 Physical examination

A complete physical exam will be performed at Visit 1 (Screening) Visit 8 (Week 26) and Visit 13 (Week 104). “Normal”, “Abnormal” or “Not done” as determined by the Investigator will be reported in the e-CRF by body system.

2.1.4.7 Electrocardiogram variables

12-lead ECGs will be performed at Visit 2 (Run-in), Visit 8 (Week 26) and Visit 13 (Week 104). ECG status of “normal” or “abnormal” will be reported in the e-CRF as determined by the investigator.

2.1.4.8 Bone Mineral Density

Bone mineral density at lumbar spine, total hip, and femoral neck will be assessed in all patients using DXA. Baseline DXA scans for BMD assessment will be performed during run-in (between week -2 [Visit 2] and Baseline [Visit 3]) and centrally reviewed to confirm eligibility. To assess percent change from Baseline in BMD, post-Baseline DXA scans will be performed within 2 weeks prior to the on-site visits at week 26 (Visit 8), week 52 (Visit 10), and week 104 (Visit 13). In exceptional situations, if justified based on Investigator's assessment, the DXA scan can be performed up to a maximum of 7 days after the scheduled visit. All BMD assessments will be performed locally with central review.

2.2 DISPOSITION OF PATIENTS

This section describes patient disposition for both patient study status and the patient analysis populations.

Screened patients are defined as all patients who signed the informed consent.

Randomized patients consist of all patients with a signed informed consent form who have had a treatment kit number allocated and recorded in the IRT database, regardless of whether the treatment kit was used or not.

For patient study status, the total number of patients in each of the following categories will be presented in the clinical study report using a flowchart diagram or summary table:

- Screened patients.
- Run in patients: patients who has a run-in kit allocated and recorded in IRT database.
- Screen failure patients (including failures during run-in) and reasons for screen failure.
- Nonrandomized but treated patients.
- Randomized patients.
- Randomized but not treated patients.
- Randomized and treated patients.
- Patients who complete the 26-week double-blind core treatment period (see [Section 2.5.4](#)) as scheduled.
- Patients who did not complete the 26-week double-blind core treatment period as scheduled and the reasons for permanent treatment discontinuation.
- Patients who complete the 104-week double-blind entire treatment period as scheduled.
- Patients who did not complete the 104-week double-blind entire treatment period as scheduled and the reasons for permanent treatment discontinuation.
- Patients who complete the study as scheduled.

- Patients who did not complete the study as scheduled and the reasons for study discontinuation.
- Patients' end of study status at Week 26 (ongoing, discontinued) and corresponding end of 26-week core treatment status (ongoing, discontinued).
- Patients' end of study status (completed, not completed) and corresponding end of entire treatment status (completed, not completed).
- Status at last study contact.

For screened, run in, screen failure, and nonrandomized but treated patients, percentages will be calculated using the number of screened patients as the denominator. All other categories of patients will be presented by treatment group and the percentages will be calculated using the number of randomized patients within each treatment group as the denominator. Reasons for treatment discontinuation will be supplied in tables giving numbers and percentages by treatment group. Patients prematurely discontinued from treatment and/or study, along with reasons for discontinuation, will also be listed.

A summary of the distribution of patients by country and center will also be provided (overall number of patients screened, run-in, randomized, , as well as number of patients randomized and treated, discontinued from study treatment, and discontinued from study for each treatment for overall patients and by treatment group).

Patients treated but not randomized, patients randomized but not treated and patients randomized but not treated as randomized will be identified and described in separate listings. The patient randomized but not treated as randomized will be part of efficacy and safety analyses (see [Section 2.3](#)). Patients randomized but not treated will be included in efficacy analysis. Safety data of patients treated but not randomized will be reported separately.

The randomization strata [HbA1c at Screening ($\leq 8.5\%$, $> 8.5\%$) and sex (Male, Female) assigned by IRT will be summarized. The percentages will be calculated using the number of randomized patients as the denominator. The discrepancy between the strata assigned by IRT and the information reported on e-CRF will be listed for all randomized patients.

Kaplan-Meier (KM) plots of the cumulative incidence of double-blind IMP discontinuations due to any reason and due to AEs respectively will be provided for the 104-week double-blind entire treatment period only (see [Section 2.5.4](#)). A listing of these patients, along with the reason for discontinuation treatment, study completion status and the reason for discontinuation study, will be provided.

All important deviations including randomization and drug dispensing irregularities will be summarized in tables giving numbers and percentages of deviations by randomized treatment group.

Additionally, the analysis populations for safety and efficacy defined in [Section 2.3](#) will be summarized in a table by number of patients on the randomized population.

- Efficacy population: intent-to-treat (ITT) population.

- Safety population.

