### **10.3.3 List of criteria for permanent treatment discontinuation**

The patients may withdraw from treatment with the IMP if they decide to do so, at any time and irrespective of the reason, or this may be the Investigator's decision. Patients should discuss stopping study medication with the site before doing so, to allow for questions to be addressed, glycemic therapy to be adjusted, and a follow-up assessment to be arranged. All efforts should be made to document the reason(s) for treatment discontinuation and this should be documented in the eCRF.

The following reasons lead to permanent discontinuation:

- At the patient's own request (ie, withdrawal of consent for treatment).
- If, in the Investigator's opinion, continuation with the administration of the study treatment would be detrimental to the patient's well-being.
- Intercurrent condition that requires permanent discontinuation of the study treatment as long as the abnormality persists and if the casual relationship of the concerned event and the IMP is possible (according to the Investigator's best medical judgment).
- BMD decrease of >7% from Baseline.
- Specific request of the Sponsor.

Any abnormal laboratory value or ECG parameter will be immediately rechecked to confirm the result before making a decision of permanent discontinuation of the IMP for the concerned patient.

For patients who prematurely discontinue the IMP, the assessments planned at EOT visit ([Section 1.2](#)) will be performed at the Premature EOT Visit scheduled preferably prior to treatment discontinuation or as soon as possible after the time of discontinuation (at the latest at the next scheduled on-site visit), and a Follow-up Visit 2 weeks ( $\pm 3$  days) after the last dose of IMP. In addition, every effort will be made to have the patient return to the site at the time corresponding to their scheduled visits, particularly the Week 26 Visit and Week 104 Visit. If the patient does not agree to site visits, he or she will be contacted by telephone to inquire about safety status and collect AE data. The reason(s) for IMP discontinuation will be clearly specified. This Premature EOT assessment may occur at a regularly scheduled or at an unscheduled visit.

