1 OVERVIEW AND INVESTIGATIONAL PLAN

1.1 STUDY DESIGN AND RANDOMIZATION

This is a Phase 3, multicenter, randomized, double-blind (single-blind Run-in Phase), placebo-controlled, parallel-group stratified study.

All patients will have a Screening Period comprised of an up to 2-week Screening Phase and a 2-week, single-blind placebo Run-in Phase prior to randomization. Following randomization, patients will have a 104-week double-blind Treatment Period (26-week double-blind core treatment period followed by a 78-week double-blind extension treatment period), and a 2-week post-treatment Follow-up period. Patients who prematurely discontinue the study treatment are expected to continue in the study to continue performing their respective study assessments, especially HbA1c and BMD, until the time of the last visit planned in the protocol.

Patients will be centrally randomized (using permuted block randomization schedule) via an Interactive Response Technology (IRT) in a 1:1:1 ratio to 1 of the 3 treatment groups:

- Sotagliflozin 400 mg.
- Sotagliflozin 200 mg.
- Placebo.

The randomization will be stratified by hemoglobin A1c (HbA1c) at the screening visit ($\leq 8.5\%$, $>8.5\%$) and sex (Male, Female).

It is anticipated to randomize a total of approximately 360 patients (120 per treatment group).

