
For time to event analysis/KM plot, time to event (eg, treatment discontinuation, rescue therapy, hypoglycemia, etc) is defined as the number of days from the date of the first administration of double-blind IMP (or the date of randomization if not exposed) to the start date of the first occurrence of the event during the respective analysis period.

Patients who did not experience any event during the respective analysis period are considered censored observations. The censoring rules are defined below:

Time to event	Censoring date at Week 26 (1st step analysis)	Censoring date at EOT/EOS (2nd step analysis)
Treatment discontinuation due to any reason	Not applicable	EOT
Treatment discontinuation due to AE	Not applicable	EOT
Time to rescue	min (EOT, Date of W26 visit)	EOT
Time to severe or documented hypoglycemia	min (EOT+1, EOS, Date of W26 visit). See Section 3	Min (EOT+1, EOS)

Note: (1) Day 182 will be used if Date of Week 26 visit (or date of W26/re-allocated W26) is not available.

(2) Date of EOS will be used if date of EOT is not available; Last contact date will be used if date of EOS is not available.

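### The Kaplan-Meier plot of stopping drug due to AEs censors patients who stop for other reasons, so it is not the cumulative incidence it is labelled as and can overstate AE discontinuation slightly

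*SAP*

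**What the plan says.** SAP 2.2 (Disposition of patients) plans two curves: "Kaplan-Meier (KM) plots of the cumulative incidence of double-blind IMP discontinuations due to any reason and due to AEs respectively will be provided". They are given "for the 104-week double-blind entire treatment period only".

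SAP 2.5.4 (Windows for time points, time-to-event analysis) sets the censoring rule: "Patients who did not experience any event during the respective analysis period are considered censored observations". Its table has a row for "Treatment discontinuation due to AE", marked not applicable at Week 26 and with EOT as the censoring date in the second-step analysis. Neither document names a competing-risk estimator.

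The plan also provides crude summaries. In SAP 2.2, "Reasons for treatment discontinuation will be supplied in tables giving numbers and percentages by treatment group", and "the percentages will be calculated using the number of randomized patients within each treatment group as the denominator". A patient listing gives the reason for each stop. SAP 2.4.5.3 adds n (%) of patients with treatment-emergent AEs leading to permanent discontinuation.

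**The concern.** Censoring in a Kaplan-Meier estimate assumes that the censored patient could still have the event later. A patient who has permanently stopped drug cannot later stop it because of an AE. The protocol allows several stops that need not involve an AE: patient or sponsor request (10.3.3), withdrawal from drug after the code is broken (8.3.2) and continued poor compliance (8.7.1). For the AE curve these are competing events. One minus Kaplan-Meier estimates how many would stop for an AE if no other kind of stop existed, which is not the quantity named in SAP 2.2. The any-reason curve does not have this problem, because every stop is its event.

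At stake is one figure showing when AE discontinuations occur over 104 weeks. It can end above the percentage in the reasons table of the same report. The excess depends on each arm's non-AE stops, so the distance between the arms on the plot can also change. Unequal non-AE stopping is possible: protocol 4.6 notes a risk of insufficient glucose control, especially on placebo. Rescue with continued study drug (protocol 8.2.2) may reduce any such imbalance.

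**Working it through.** **No figure to reproduce.** The documents state no rate of discontinuation, for AEs or otherwise. The only attrition figure is the 30% missing rate for BMD in the sample-size section (protocol 11.1, SAP 1.3). Missing data are not the same as stopping drug, so 30% serves here only as an upper reference for total stops in the single-arm table. All rates below are assumptions.

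**Direction.** Let d(t) be the AE stops at time t and Y(t) the patients still on drug.
- Aalen-Johansen adds S_all(t−) × d(t)/Y(t), where S_all is the probability of not having stopped for any reason.
- One minus Kaplan-Meier adds S_AE(t−) × d(t)/Y(t), where S_AE treats non-AE stops as censored.

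S_AE is never below S_all, so one minus Kaplan-Meier is never below the cumulative incidence. The two separate only when an AE stop follows a non-AE stop.

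**Size in one arm.** Assume constant cause-specific hazards over 104 weeks and follow-up of every patient to a stop or to completion. Let a be the true AE proportion and o the proportion stopping for other reasons.
- Total cumulative hazard: H = −ln(1 − a − o).
- AE part: h = H × a/(a + o).
- Plotted value: 1 − exp(−h).

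Example: for a = 0.10 and o = 0.20, H = −ln(0.70) = 0.357, h = 0.357 × 0.10/0.30 = 0.119, and 1 − exp(−0.119) = 11.2%, against a true 10.0%.

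| AE (true) | Other | Plotted | Excess, points |
|---|---|---|---|
| 5% | 5% | 5.1% | 0.13 |
| 5% | 10% | 5.3% | 0.27 |
| 5% | 15% | 5.4% | 0.43 |
| 5% | 25% | 5.8% | 0.77 |
| 8% | 22% | 9.1% | 1.07 |
| 10% | 20% | 11.2% | 1.21 |
| 15% | 15% | 16.3% | 1.33 |

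The relative excess runs from about 3% to 15%. A simulation of the 8%/22% case gave 8.1% crude and 9.1% plotted.

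**Timing.** For 8% AE and 22% other, the plotted value is 8.0% if all AE stops come first. It is 0.08/(1 − 0.22) = 10.3% if all other stops come first.

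**Gap between arms (same formula).**

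| Arm A: AE/other | Arm B: AE/other | True gap | Plotted gap |
|---|---|---|---|
| 8%/12% | 5%/12% | 3.0 | 3.2 |
| 8%/25% | 5%/10% | 3.0 | 4.0 |
| 8%/10% | 5%/25% | 3.0 | 2.7 |
| 8%/25% | 8%/5% | 0.0 | 1.0 |

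**Scale.** With the planned 120 patients per arm, 1.2 points is 0.012 × 120 = 1.4 patients. For two arms at 8%, the standard error of the difference is √(2 × 0.08 × 0.92/120) = 3.5 points, so the spurious 1.0-point gap is about 0.3 standard errors.

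**The case against.** The strongest reply is that the undistorted figures are already planned. The reasons table in SAP 2.2 uses randomized patients as its denominator, and the AE summaries in SAP 2.4.5.3 use the safety population. Neither censors anyone. The plot carries no test, interval or decision rule, and the protocol's disposition section does not ask for it. All of this stands, and it limits the point to one descriptive figure. It does not remove the mismatch between label and estimator. The tables give totals and cannot correct the shape of the curve over time.

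It is also fair to say that the size rests wholly on assumed rates and is small against sampling error. That stands too.

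Two stronger readings are tempting, and neither holds.
- A reader might infer that the curve always exceeds the crude percentage. It need not: if AE stops come before other stops, the two agree.
- A reader might infer that the excess is always larger in the arm with more non-AE stops. It also depends on the AE rate and on timing. In the table above, the excess falls from 1.33 to 1.21 to 0.77 points as other stops rise from 15% to 20% to 25%, because the AE rate falls at the same time. Only with AE rate and timing held fixed does the excess grow with non-AE stopping, as the four rows at 5% AE show.

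**Conclusion.** The point holds as a minor one. As written, the AE curve is not a cumulative incidence: it is never below the true value, and it lies above it whenever AE stops follow non-AE stops. Under constant hazards, AE stops of 5 to 15%, other stops of 5 to 25% and a total of 10 to 30%, the overstatement is about 0.1 to 1.3 points. In the scenarios tried, where total stops in an arm reach 33%, the gap between arms moves by about 1 point or less, in either direction.

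A reader might go further and infer that the plan's tolerability comparison is biased, or biased for or against sotagliflozin. The documents do not support that. They give no discontinuation rates by arm or reason, the n (%) tables are unaffected, and no efficacy or safety conclusion is tied to the plot.

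**What to change.** For the AE plot in SAP 2.2, replace one minus Kaplan-Meier with the Aalen-Johansen cumulative incidence function.
- **Event:** stopping drug due to an AE, including a fatal AE.
- **Competing event:** stopping for any non-AE reason, including death not due to an AE. Naming all deaths as competing would remove fatal AEs from the AE curve.
- **Censoring:** only patients who complete treatment or are still on drug.

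Amend the AE row of the censoring table in SAP 2.5.4 to match, and keep one minus Kaplan-Meier for the any-reason curve. If the reasons table uses the same patients and classifies fatal AEs the same way, the AE curve will end at its crude percentage once every patient has been followed to a stop or to completion.

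The cost is a few lines of SAP wording and a standard SAS option or macro. The reasons and dates for stopping are already collected. A lighter alternative is to relabel the existing curve as a cause-specific Kaplan-Meier estimate, state that it is not a cumulative incidence, and refer readers to the n (%) table.
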